## 7.9.2 Other Efficacy parameter(s)

The other efficacy parameters are as follows:

- **Weekly CSBM +1 Responder:** For each week in the Treatment Period, a Weekly CSBM +1 Responder is a patient who has an increase from baseline of at least 1 in the CSBM weekly rate for that week. If a patient did not enter information into the eDiary on at least

4 days for a particular Treatment Period week, the patient will not be considered a Weekly CSBM +1 Responder for that week.

- **6/12 Week CSBM +1 Responder:** A 6/12 Week CSBM +1 Responder is a patient who meets the Weekly CSBM +1 Responder criteria for at least 6 out of the 12 weeks of the Treatment Period.
- **9/12 Week CSBM +1 Responder:** A 9/12 Week CSBM +1 Responder is a patient who meets the Weekly CSBM +1 Responder criteria for at least 9 out of the 12 weeks of the Treatment Period.
- **CSBM (SBM) within 24 Hours of Receiving the First Dose of Study Drug:** Date and time of first dose and date and time of first CSBM (SBM) is used to determine whether a CSBM (SBM) is occurred within 24 hours after the patient took the first dose of study drug.
- **Change from Baseline in 12-week CSBM Frequency Rate:** A patient's 12-week CSBM frequency rate will be the CSBM rate (CSBMs/week) calculated over the 12 weeks of the Treatment Period.
- **Weekly Abdominal Pain Responder:** A Weekly Abdominal Pain Responder is a patient who has a decrease in the weekly average of the abdominal pain score of at least 30% compared with the baseline average. If a patient did not enter information into the eDiary on at least 4 days for a particular Treatment Period week, the patient will not be considered a Weekly Abdominal Pain Responder for that week.
- **6/12 Week Abdominal Pain Responder:** A 6/12 Week Abdominal Pain Responder is a patient who meets the Weekly Abdominal Pain Responder criteria for at least 6 out of the 12 weeks of the Treatment Period.
- **9/12 Week Abdominal Pain Responder:** A 9/12 Week Abdominal Pain Responder is a patient who meets the Weekly Abdominal Pain Responder criteria for at least 9 out of the 12 weeks of the Treatment Period.
- **Weekly Abdominal Symptom Score Responder:** A Weekly Abdominal Symptom Score Responder is a patient who has a decrease in the weekly average of the Abdominal Symptom Score of at least 30% compared with the baseline average. If a patient did not enter information into the eDiary on at least 4 days for a particular Treatment Period week, the patient will not be considered a Weekly Abdominal Symptom Score Responder for that week.
- **6/12 Week Abdominal Symptom Score Responder:** A 6/12 Week Abdominal Symptom Score Responder is a patient who meets the Weekly Abdominal Symptom Score Responder criteria for at least 6 out of the 12 weeks of the Treatment Period.

- **9/12 Week Abdominal Symptom Score Responder:** A 9/12 Week Abdominal Symptom Score Responder is a patient who meets the Weekly Abdominal Symptom Score Responder criteria for at least 9 out of the 12 weeks of the Treatment Period.
- **Change from Baseline in 12-week Abdominal Pain:** Abdominal pain is measured daily using an 11-point NRS. The patient's abdominal pain score for the Treatment Period is the average of the non-missing daily worst abdominal pain scores reported by the patient during the 12-week Treatment Period.
- **Percent Change from Baseline in 12-week Abdominal Pain:** Percent change will be calculated as the  $100 * \frac{\text{Change from Baseline in Abdominal Pain}}{\text{baseline Abdominal Pain score}}$ .
- **Change from Baseline in 12-week SBM Frequency Rate:** A patient's 12-week SBM frequency rate will be the SBM rate (SBMs/week) calculated over the 12 weeks of the Treatment Period.
- **Change from Baseline in 12-week Stool Consistency:** Stool consistency is measured using the 7-point BSFS. The patient's BSFS score for the Treatment Period is the average of the non-missing BSFS scores from the SBMs reported by the patient during the 12-week Treatment Period.
- **Change from Baseline in 12-week Straining:** Straining is measured using a 5-point ordinal scale. The patient's straining score for the Treatment Period is the average of the non-missing straining scores from the SBMs reported by the patient during the 12-week Treatment Period.
- **Change from Baseline in 12-week Abdominal Discomfort:** Abdominal discomfort is measured daily using an 11-point NRS. The patient's abdominal discomfort score for the Treatment Period is the average of the non-missing daily abdominal discomfort scores reported by the patient during the 12-week Treatment Period.
- **Change from Baseline in 12-week Abdominal Bloating:** Abdominal bloating is measured daily using an 11-point NRS. The patient's abdominal bloating score for the Treatment Period is the average of the non-missing daily abdominal bloating scores reported by the patient during the 12-week Treatment Period.
- **Change from Baseline in 12-Week Abdominal Symptom Score:** The patient's abdominal symptom score for the Treatment Period is the average of the non-missing daily abdominal symptom scores reported by the patient during the 12-week Treatment Period. A patient's daily abdominal symptom score is calculated as the average of the daily abdominal pain, abdominal bloating, and abdominal discomfort. If two or more of the individual daily abdominal symptoms are missing, then the Abdominal Symptom Score for that day will be missing.

- **Change from Baseline in 12-Week Constipation Severity:** Constipation severity is measured weekly using a 5-point ordinal scale. The patient's constipation severity score for the Treatment Period is the average of the non-missing weekly constipation severity scores reported by the patient during the 12-week Treatment Period.
- **Change from Baseline in 12-week IBS Symptom Severity:** IBS symptom severity is measured weekly on a 5-point ordinal scale. The patient's IBS symptom severity score for the Treatment Period is the average of the non-missing weekly IBS symptom severity scores reported by the patient during the 12-week Treatment Period.
- **Change from Baseline in 12-Week Percent of Days with Use of Rescue Medicine:** The percent of days using per-protocol rescue medicine or any other laxative, suppository, or enema during the Treatment Period will be calculated as  $100 * \frac{\text{the number of days rescue medicine was used during the Treatment Period}}{\text{the total number of days on treatment}}$ .
- **Treatment Satisfaction:** Treatment satisfaction is measured on a 5-point ordinal scale. Treatment satisfaction will be analyzed separately at each post-dose visit.
- **Adequate Relief:** Assessment of adequate relief during the previous 7 days is measured on a binary scale (yes/no). Assessment of adequate relief will be analyzed separately at each post-dose visit.
- **6/12 Week Adequate Relief Responder:** A 6/12 Week Adequate Relief Responder is a patient who reports Adequate Relief for at least 6 out of the 12 weeks of the Treatment Period.
- **9/12 Week Adequate Relief Responder:** A 9/12 Week Adequate Relief Responder is a patient who reports Adequate Relief for at least 9 out of the 12 weeks of the Treatment Period.

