  - c. An appendectomy or cholecystectomy during the 60 days before the Screening Visit
  - d. Other major surgery during the 30 days before the Screening Visit
12. Patient has a history of cancer other than treated basal cell or squamous cell carcinoma of the skin. (Note: Patients with a history of cancer are allowed provided that the malignancy has been in a complete remission for at least 5 years before the Randomization Visit. A complete remission is defined as the disappearance of all signs of cancer in response to treatment.)
  13. Patient has a history of diabetic neuropathy.
  14. Patient has untreated hypothyroidism or treated hypothyroidism for which the dose of thyroid hormone has not been stable for at least 6 weeks at the time of the Screening Visit.
  15. Patient has a recent history (during the 12 months before the Randomization Visit) of drug or alcohol abuse. (Note: Patients with a history of drug or alcohol abuse that was diagnosed greater than 12 months before the Randomization Visit may be enrolled as long as they have exhibited no actual abuse during the 12 months before the Randomization Visit.)
  16. Patient reports a BSFS score of 6 (loose, mushy stools) for > 1 SBM or a BSFS score of 7 (watery stools) with any SBM over the 14 calendar days before the Randomization Visit and the calendar day of Randomization up to the time when data is entered into the eDiary in the clinic.
  17. Patient used Rescue Medicine (bisacodyl tablet or suppository) or any other laxative, suppository, or enema, on the calendar day before or the calendar day of the start of the Randomization Visit.
  18. Patient reported using a Prohibited Medicine (excluding laxatives, suppositories, and enemas) during the Pretreatment Period or is not willing or able to abide by the restrictions regarding use of Prohibited Medicines defined in [Appendix II](#). (Note: The use of fiber, bulk laxatives, or stool softeners [such as docusate] is acceptable provided the patient has been on a stable dose during the 30 days before the Screening Visit and plans to continue on a stable dose throughout the study.)
  19. Patient has been hospitalized for a psychiatric condition or has made a suicide attempt during the two years before the Randomization Visit.
  20. Patient has taken commercially available linaclotide or participated in a linaclotide, plecanatide, or SP-333 clinical study during the 30 days before the Screening Visit.

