#### **5.4.7 Concomitant Medicines**

A complete list of drugs that are conditionally allowed and drugs that are not allowed as concomitant medicines for either episodic or chronic use or as Rescue Medicine is provided in [Appendix II](#). During the Pretreatment and Treatment Periods, patients may use dispensed, protocol-permitted laxatives (bisacodyl tablets or suppositories) as Rescue Medicine when at least 72 hours have passed since their previous BM or when their symptoms become intolerable. In order to qualify for randomization into the Treatment Period, patients must not have used Rescue Medicine on the calendar day before the Randomization Visit and on the day of the Randomization Visit up until the time of the clinic visit. Patients must agree to refrain from using Rescue Medicine from the time they arrive at the clinic for the Randomization Visit through the calendar day after randomization.

At the Screening Visit, all ongoing medicines or investigational products taken by the patient, and past use of certain IBS-C or CIC (approved or unapproved) prescription medications

(including tegaserod [Zelnorm®], prucalopride, plecanatide, linaclotide [Linzess®] and lubiprostone [Amitiza®]), even if not ongoing at the time of the Screening Visit, will be recorded. Any over-the-counter or prescription laxatives, suppositories, or enemas used to treat IBS-C may not be used during the Pretreatment and Treatment Periods and may not be used on the calendar day before the Pretreatment Visit. Other prohibited medicines may not be used during the Pretreatment and Treatment Periods and may not be used during the 14 calendar days before the Pretreatment Visit (refer to [Appendix II](#)). Thereafter, any changes in concomitant medicines or new medicines added will be recorded on the eCRF. Concomitant medicines will be recorded at study visits throughout the entire study. Rescue Medicine will be documented by the patient via eDiary.

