IBS symptom severity is measured weekly on a 5-point ordinal scale. The patient's IBS symptom severity score for the Treatment Period is the average of the non-missing weekly IBS symptom severity scores reported by the patient during the 12-week Treatment Period.

- **Change from Baseline in 12-Week Percent of Days with Use of Per-Protocol Rescue Medicine**

The percent of days using per protocol rescue medicine or any other laxative, suppository, or enema during the Treatment Period will be calculated as the  $100 * \text{number of days rescue medicine was used during the Treatment Period} / \text{total number of days on treatment}$ .

- **Treatment Satisfaction**

Treatment satisfaction is measured on a 5-point ordinal scale. Treatment satisfaction will be analyzed separately at each post-dose visit.

- **Assessment of Adequate Relief**

Assessment of adequate relief during the previous 7 days is measured on a binary scale (yes/no). Assessment of adequate relief will be analyzed separately at each post-dose visit.

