### **6.3 HANDLING OF DROPOUTS/MISSING DATA IMPUTATION METHOD**

For responder endpoints, a patient will be deemed a weekly non-responder for all weeks following the patient's discontinuation from the study. The responder definition will be applied to the week the patient discontinues. Unless stated otherwise, missing data will not be imputed.

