### **Gaps in the eDiary Data**

If a patient does not complete either a spontaneous or evening report every day, there will be gaps in the data.

There will be no adjustments for these gaps in the eDiary data for the efficacy data analyses using an OC approach. Effectively, this means that analyses will assume that no rescue medicine use or BMs occurred during these gaps.

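### The rescue-use percentage divides reported rescue days by all days on treatment, so an unreported day on drug counts as a rescue-free day

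*SAP*

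**What the plan says.** SAP 7.9.2 defines the percentage behind the Change from Baseline in 12-Week Percent of Days with Use of Rescue Medicine as 100 times "the number of days rescue medicine was used during the Treatment Period" divided by "the total number of days on treatment". Protocol 5.7.7.3 uses the same denominator, "total number of days on treatment". Rescue use is known only from what the patient enters in the eDiary (Protocol 5.4.7; SAP 7.7).

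For days without a report, SAP 9.4.2 (Gaps in the eDiary Data) makes no adjustment and adds that "analyses will assume that no rescue medicine use or BMs occurred during these gaps". The general rule in SAP 6.3 points the same way: "Unless stated otherwise, missing data will not be imputed".

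SAP 7.7 refers the summary of rescue use to Section 7.9.2, where this is the only rescue parameter. As a continuous 12-week change from baseline, it is compared with placebo by ANCOVA with baseline as covariate (SAP 7.9.2.2).

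The baseline window runs from Day -14 to the time of randomization (SAP 7.9 and Table 6). The formula is written for the Treatment Period only, and neither document gives a denominator for the baseline percentage. Two rules restrict rescue near randomization. Exclusion 17 (Protocol 5.3.2) removes anyone who used Rescue Medicine "or any other laxative, suppository, or enema, on the calendar day before or the calendar day of the start of the Randomization Visit". Protocol 5.4.7 also requires patients to agree to "refrain from using Rescue Medicine from the time they arrive at the clinic for the Randomization Visit through the calendar day after randomization".

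**The concern.** Only reported days can enter the numerator, but every day on treatment enters the denominator. Under the gap rule, a patient who goes on taking study drug and lets the diary lapse shows falling rescue use. For stool counts the same convention works against the patient, because a gap lowers the CSBM rate. For rescue it reads as improvement.

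Nothing in the analysis plan offsets this for the rescue parameter:

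- The requirement of 4 complete evening reports (SAP 7.9) applies to weekly responder parameters.
- The multiple-imputation sensitivity analysis (SAP 7.9.1.2) also sets weeks with fewer than 4 complete evening diaries to missing. It covers the key endpoints and unspecified others, and rescue is not named.
- The rank-transformed ANCOVA list in SAP 7.9.2.2 does not include rescue.
- The missing-date rule for rescue in SAP 9.4.2 handles an entry without a date, not an absent report.

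At stake is the one planned result that shows whether rescue use differed between arms, and so whether the bowel results were obtained under similar rescue use.

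**Working it through.** The documents state no rate, SD or power for this parameter, so there is no planned figure to reproduce. The check is direct arithmetic.

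**Inputs from the documents.** Treatment lasts about 85 days (SAP Table 6). The baseline window is 14 days plus the part of Day 1 before randomization (SAP 7.9). Eligibility requires diary compliance on at least 10 of the 14 days before randomization (Protocol inclusion 12), so up to 4 of 14 may be unreported.

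**Assumptions.** True rescue use is 10%, 20% or 30% of days. The share of days unreported is 10% to 30%. An unreported day has neither a spontaneous nor an evening report. Baseline gaps are assumed to be scored as treatment gaps are.

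**1. One patient.** With 85 treatment days, 60 of them reported and 12 rescue days, the SAP formula gives 12/85 = 14.1%. Over reported days the result is 12/60 = 20.0%.

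**2. Difference between arms.** Computed % = true % × (1 − share unreported). With the same true use in both arms and 10% versus 25% of days unreported:

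| True use | 10% unreported | 25% unreported | False difference |
|---|---|---|---|
| 10% | 9.0 | 7.5 | 1.5 points |
| 20% | 18.0 | 15.0 | 3.0 points |
| 30% | 27.0 | 22.5 | 4.5 points |

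The arm that reports less appears to use less rescue.

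**3. Change from baseline.** With true use unchanged at 20%:

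- 10% unreported at baseline and 30% on treatment: 20 × 0.90 = 18.0, then 20 × 0.70 = 14.0, a false change of −4.0 points (−2.0 at 10% use, −6.0 at 30%).
- 4 of 14 days unreported at baseline and none on treatment: 20 × 10/14 = 14.3, then 20.0, a false change of +5.7 points.

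The sign therefore depends on which period is reported less well.

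**4. Reported days as denominator.** If unreported days resemble reported ones, numerator and denominator shrink together: 20 × 0.90/0.90 = 20 and 20 × 0.75/0.75 = 20. The false difference is 0.

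**5. Days on which rescue is barred (secondary).** Take an assumed 30% use, unchanged, and full adherence to the restriction after randomization. Treatment computes to 30 × 83/85 = 29.3. Baseline depends on the undefined denominator:

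- Day -1 only, of 14 days: 30 × 13/14 = 27.9, a false change of +1.4 points.
- Day -1 and Day 1, of 15 dates: 30 × 13/15 = 26.0, a false change of +3.3 points.

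This is the same in every arm. If true treatment-period use is 15% on placebo and 10% on active, the difference of −5.00 becomes −5 × 83/85 = −4.88, a shrinkage of 2/85 = 2.4%.

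**The case against.** The strongest reply is that reporting is supported and visible. The coordinator verifies diary compliance at the Week 4, Week 8 and Week 12 visits and gives reminders at the first two (Protocol 5.5.1). SAP 7.8 tabulates compliance by treatment group, by week and for the whole period. A reader might infer that diary keeping goes unchecked after randomization; the documents do not support that. But these measures would only reveal a difference in reporting. They do not remove it from the percentage.

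Second, the exposure is narrower than the formula suggests. For a patient who withdraws, the Treatment Period ends at the last dose (SAP 9.2), and a last-dose date that cannot be obtained is set to the last eDiary entry (SAP 9.6). Rescue is also entered as it happens, so a missed evening report does not erase an entry already made. The bias therefore needs patients who keep dosing while reporting less. This stands as a limit on size. It is not a cure, because after a missed evening report recall reaches back only to 7 PM the previous night (SAP 9.4.1), so most of a fully missed day is lost.

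Third, the gap rule is a disclosed observed-case convention, and the use and reporting rates above are not from the documents. Both are true. Disclosure does not change what the formula computes, and the figures are illustrations only.

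Fourth, a reported-days denominator has its own bias: it drops rescue entered on days without an evening report and assumes that unreported days resemble reported ones. This is fair, and is why the all-days version should be kept beside it.

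**Conclusion.** The point holds. Followed as written, the plan scores unreported on-drug days as rescue-free. The comparison with placebo is biased only if reporting differs between arms, and the change from baseline only if reporting differs between the two periods. For the 10% versus 25% unreported contrast, the false difference is 1.5 to 4.5 points over assumed true use of 10% to 30%.

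Three stronger readings are tempting, and the documents do not support them:

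- **That the error must favor linaclotide, or must always show less rescue over time.** Nothing in the documents says which arm will report less, and eligibility allows gaps at baseline too.
- **That the rescue-free days around randomization distort the treatment comparison.** They apply equally to all arms and shrink the placebo difference by about 2.4%. Their effect is on the within-arm change, and its size turns on a baseline denominator that the plan does not define.
- **That the efficacy conclusions are at risk.** This is one of many other efficacy parameters with nominal p-values (SAP 6.1), and no key parameter uses this percentage.

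It is worth correcting because the change is small and this is the planned evidence on rescue use by arm.

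**What to change.** In SAP 7.9.2, replace the formula with 100 × (rescue days among days with a completed evening report) / (days with a completed evening report), using the definition of a complete evening report in SAP 7.8. That report asks whether all rescue use for the day has been entered (SAP 5.3.1), so a completed one supports a true zero. State that the same definition applies to the baseline window.

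Keep the all-days version as a sensitivity analysis, since it retains rescue entered on days without an evening report. Present the SAP 7.8 compliance table beside both.

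As a minor addition, Day -1 and the part of Day 1 before randomization can be left out of the baseline percentage. Do not delete rescue recorded on Day 1 after randomization or on Day 2: patients only agree to refrain then, so use can occur and be recorded.

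The cost is one formula, its program and one extra table. No new data are needed and the rescue rule does not change. The downsides are that event-driven entries on days without an evening report leave the main version, and that unreported days are taken to resemble reported ones.

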### 7.9.2.1 Sustained Responders

Select 9/12 Week and 6/12 Week responder parameter will also be assessed for as sustained response to determine if the treatment effect is maintained during weeks 9 to 12 of the treatment period. A 9/12 Week Sustained Responders is a patient meeting the 9/12 Week Responder definition, plus are weekly responders for 3 of the last 4 weeks (weeks 9-12) of the treatment period. A 6/12 Week Sustained Responders is a patient meeting the 6/12 Week Responder definition, plus are weekly responders for 2 of the last 4 weeks (weeks 9-12) of the treatment period. The Sustained Responder definition will be applied to the following response endpoints:

- APC+1 Responder
- CSBM+1 Responder
- Abdominal Pain Responder

### 7.9.2.2 Analyses of Other Efficacy Parameters

All categorical responder parameters (e.g., Weekly CSBM +1 Responder) and CSBM (SBM) with 24-hours of first dose, will be analyzed utilizing the same methods defined above for the key efficacy measure 6/12 Week APC +1 Responder.

All continuous change-from-baseline in 12-week efficacy parameters will be evaluated using an ANCOVA model with treatment group and geographic region as fixed-effect terms and baseline value as a covariate. Least-squares (LS) means for each treatment group, LS mean differences between each linaclotide dose and placebo and their corresponding confidence intervals, and p-values for the pairwise comparisons versus placebo will be presented. [REDACTED]

[REDACTED]

For Treatment Satisfaction, inferential testing will be evaluated employing a MMRM framework with week (categorical), treatment, and week-by-treatment fixed effects, and patient as the random effect. The covariance structure will be unstructured. Pairwise comparisons between each treatment group and placebo will be performed overall and at each visit. Associated LSM means, LSM means differences and confidence intervals will be presented.

For Change from Baseline in 12-Week CSBM, SBM, Stool Consistency (BSFS and 5 point ordinal score), Abdominal Pain, Abdominal Discomfort, Abdominal Bloating, and the Abdominal Symptom Composite Score, sensitivity analyses will be performed by applying the same ANCOVA model to the rank-transformed data. Change and baseline values will be ranked based on the normalization method of Blom with ties set to the mean. If the results of the sensitivity analysis show consistency with those obtained from the original analysis, only results from the original ANCOVA will be reported.

For Change from Baseline in weekly SBM, Stool Consistency (BSFS and 5 point ordinal score), Abdominal Discomfort, Abdominal Bloating, and the Abdominal Symptom Composite Score, an ANCOVA with treatment and geographic region as fixed effects and baseline as a covariate will be fit. All pairwise comparisons performed for the 12-week analyses will be performed for each week.

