Linaclotide was well-tolerated in these trials.  There were no deaths. One patient died during the Screening Period but never received either linaclotide or placebo. There were a total of 15 SAEs in the two trials. There were 9 (1.1%) SAEs in placebo-treated patients and 6 (0.7%) SAEs in linaclotide-treated patients. Overall, there was no obvious pattern in the types of SAEs experienced in either the placebo or linaclotide group. There were no SAEs of diarrhea. Treatment-emergent AEs (TEAEs) occurred in 54.9% of placebo-treated and 60.8% of linaclotide-treated patients. Diarrhea was the most frequent TEAE and was reported in 3.0% of patients treated with placebo and 19.8% of patients treated with linaclotide. Diarrhea was generally mild to moderate in severity. Diarrhea resulted in the discontinuation of 0.4% of patients treated with placebo and 5.3% treated with linaclotide. Human studies have not been conducted with the DR formulations of linaclotide. As the IR and DR formulations have the

same active ingredient, similar gastrointestinal side effects (diarrhea, abdominal pain, abdominal distension, and flatulence) may be expected. However, the frequency and severity of these effects remain to be determined.

Refer to the Investigator's Brochure for a more detailed description of the chemistry, pharmacology, efficacy, and safety of linaclotide, based on studies conducted in animals, healthy volunteers, and in patients with IBS-C and CIC and its relevance to the delayed release formulations.

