### 7.9.1.1 Analyses of the Key Efficacy Parameters

All analyses of the key primary efficacy endpoints will be performed on the ITT Population.

For each continuous weekly change-from-baseline measure defined above, inferential testing of the change from baseline will be evaluated employing a MMRM framework with week (categorical), treatment, geographical region, and week-by-treatment fixed effects, and baseline value as a covariate. A compound symmetry covariance structure will be used to model the covariance of within-patient results. Exploratory analyses with unstructured and autoregressive (1) covariance structures will also be considered for planning purposes.

The overall dose response within each DR formulation will be conducted by employing an overall trend test (i.e., linear contrast, see [Appendix VI](#)) for each formulation to test for a monotonically increasing dose response within the MMRM. Overall treatment effect pairwise comparisons will be performed between each linaclotide treatment and placebo. [REDACTED]

[REDACTED]

Pairwise treatment comparisons with placebo will be performed at each week utilizing the same MMRM models.

The efficacy analysis of 6/12 Week APC+1 Responder rate will be performed by using a CMH test controlling for geographic region for each DR formulation (i.e., 1. DR1 and Placebo; 2. DR2 and Placebo). The overall trend test will be assessed via the CMH correlation statistics to test for

a monotonically increasing dose response within the formulation. Pairwise comparisons between each linaclotide dose and placebo will be performed.

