withdrawn patient’s Treatment Period, and all subsequent Treatment Period weeks will be missing for that patient.

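### Weekly SBM, stool consistency, discomfort, bloating and composite comparisons use separate by-week ANCOVAs, so late-week results can be biased if dropout depends on response; an MMRM would be a cheap improvement

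*SAP*

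**What the plan says.** The last paragraph of SAP 7.9.2.2 covers weekly change from baseline in SBM, stool consistency (both scales), discomfort, bloating and the abdominal symptom composite. It says "an ANCOVA with treatment and geographic region as fixed effects and baseline as a covariate will be fit" and adds "All pairwise comparisons performed for the 12-week analyses will be performed for each week". The model has no week term and no within-patient covariance.

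For weekly pain and CSBM, SAP 7.9.1.1 tests change from baseline by "employing a MMRM framework with week (categorical), treatment, geographical region, and week-by-treatment fixed effects". There, "A compound symmetry covariance structure will be used to model the covariance of within-patient results", with unstructured and AR(1) structures as exploratory alternatives. Treatment Satisfaction, also in 7.9.2.2, gets an MMRM with unstructured covariance.

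On missing data, SAP 6.3 says "Unless stated otherwise, missing data will not be imputed". SAP 9.2, in the text after Table 6, says that once a patient withdraws, "all subsequent Treatment Period weeks will be missing for that patient". SAP 9.4.2 and 9.4.3.1 treat on-treatment diary gaps as time without bowel movements and do not shorten the week. SAP 7.9.1.2 describes a placebo-based multiple imputation, to be used only if judged necessary, for the key endpoints and some others that it does not name.

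Protocol 5.7.7.4 specifies only the 12-week ANCOVA for these continuous measures. SAP Section 8 does not list the added weekly ANCOVAs as a change.

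**The concern.** A Week 12 ANCOVA fitted alone on observed patients gives no weight to Weeks 1 to 11 of a patient who has left. If leaving depends on how the patient was responding, the patients who remain in each arm are a selected group, and their difference need not equal the difference among all randomized patients. A likelihood-based repeated-measures model conditions on the earlier reports and, with a suitable covariance, removes this bias when dropout depends only on observed data.

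The composite is the mean of pain, bloating and discomfort (SAP 7.9.2 and 9.4.4), yet its weekly test handles dropout differently from the weekly test of its own pain component. A difference in time course between pain and bloating could therefore come partly from the method. In a dose-range-finding study, where dropout may differ by dose, that could colour how doses are compared on these symptoms.

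**Working it through.** **Plan's own figures.** The plan states no figure for the weekly ANCOVAs. The sample-size figures in SAP Section 4 supply an effect and an SD, so they were reproduced first.
- Trend: |(-3)(-1.196) + (-1)(-1.586) + (1)(-1.975) + (3)(-1.975)| = 2.726. SE = 1.73 × √(20/65) = 0.960. Ratio 2.841; Φ(2.841 - 1.960) = 81.1%, against the stated 81%.
- Pairwise: 0.779 / (1.73 × √(2/65)) = 2.567; Φ(2.567 - 1.960) = 72.8%, against the stated 73%.

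**Simulation inputs.**
- From the SAP: SD 1.73 and a true Week 12 difference of -1.975 - (-1.196) = -0.779. These are pain values, borrowed because the documents give no effect or SD for the five endpoints.
- Assumed: 40,000 patients per arm, so that bias rather than chance is seen (Monte Carlo SE about 0.012 to 0.02); effect building to full size over four weeks; baseline SD 1.7; within-patient correlation either compound symmetry 0.65 or AR(1) 0.93.
- Assumed dropout: the weekly logit is a constant, or a constant plus a slope (0.4 or 0.8) times baseline or the previous week's value. In the differential cases only placebo patients leave for poor response, and active patients leave at random.

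**Results with compound-symmetry data.** Bias = (0.779 - |estimate|) / 0.779.

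| Dropout mechanism | Placebo / active dropout | By-week ANCOVA | MMRM, true covariance | ANCOVA bias toward null |
|---|---|---|---|---|
| Random | 18% / 18% | -0.761 | -0.761 | none beyond simulation error |
| Depends on baseline | 21% / 21% | -0.790 | -0.791 | none beyond simulation error |
| Response, same rule, low | 11% / 9% | -0.758 | -0.774 | 3% |
| Response, same rule, moderate | 25% / 21% | -0.729 | -0.774 | 6% |
| Response, same rule, strong | 39% / 29% | -0.613 | -0.766 | 21% |
| Differential, moderate | 23% / 18% | -0.596 | -0.785 | 23% |
| Differential, strong | 34% / 18% | -0.296 | -0.772 | 62% |

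The 3% in the low case is about the size of the simulation error. The ANCOVA-to-MMRM gap in the same data, 0.016, is the steadier guide.

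**AR(1) data.** The ANCOVA results are similar (-0.762 low, -0.593 and -0.318 differential). An MMRM with the SAP's compound symmetry overshoots in the two differential cases, at -0.817 and -0.848, where the true covariance gives -0.780 and -0.763.

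**Direction.** The only discontinuation figures in the documents come from earlier trials of the IR form: "Diarrhea resulted in the discontinuation of 0.4% of patients treated with placebo and 5.3% treated with linaclotide" (Protocol Section 3). With 5.3% active and 0.4% placebo dropout, all driven by response, the observed-case Week 12 difference is -0.67 to -0.73 if strong responders leave and -0.83 to -0.88 if poor responders leave. A hand check gives an outer range. If the most extreme 5.3% leave on a measure correlated r with Week 12, the remaining mean shifts by r × 1.73 × φ(1.616)/0.947 = r × 1.73 × 0.114. That is 0.13 at r = 0.65 and 0.18 at r = 0.93, in either direction.

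**The case against.** The case against is substantial, and most of it stands as a limit on the point.

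- **Bias is conditional.** A reader might infer that the late-week effects are biased as planned. The documents give neither a dropout rate nor a mechanism for this trial, and random or baseline-driven dropout produces no bias. Only the possibility is supported.
- **Direction is open.** A reader might infer that effects will be understated because strong responders leave drug with diarrhea. The diarrhea figures concern the IR form, and Protocol Section 3 hypothesizes that the DR forms will limit fluid secretion. The same section expects abdominal pain and distension as possible side effects, so patients leaving active treatment could be worse on discomfort, bloating and the composite. Protocol 5.3.3 lists lack of efficacy as a discontinuation reason for any patient, not by arm.
- **SBM differs.** An on-treatment patient who stops reporting stays in the weekly SBM analysis with bowel movements counted as zero. Stool consistency is also missing in any week without an SBM, which is not dropout.
- **The plan's MMRM is not a clean benchmark.** Its compound symmetry can itself mislead when correlation decays over time, as the AR(1) results show.
- **A safeguard exists.** The placebo-based imputation could be extended to these endpoints. It is optional, however, and does not name them; the missing-data sensitivity analyses in Protocol 5.7.7 are for the key endpoints only.
- **The stakes are low.** These are non-key endpoints with nominal p-values (SAP 6.1). The 12-week ANCOVAs use whatever a dropout reported before leaving, and the efficacy rule rests on the key trend tests.

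What remains is that the plan uses the weaker of two methods it already contains, without giving a reason, on endpoints for which response-related dropout is plausible.

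**Conclusion.** The point holds as a conditional weakness of minor priority. Late-week comparisons for discomfort, bloating, the composite and stool consistency, and for SBM after the last dose, can be biased if dropout depends on post-baseline response. In the main simulations the size runs from nil, through about 3% at about 10% dropout under a common rule, to 20% or more when dropout is heavy or strongly differential. The rate alone does not fix the size: with about 12% dropout per arm and opposite mechanisms in the two arms, the observed-case estimate was -0.55 to -0.57 against a likelihood-based -0.78 to -0.79.

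All of this rests on assumed rates, mechanisms and correlations, and on the pain effect and SD standing in for endpoints on other scales. Neither a definite bias nor a definite direction can be claimed from the documents.

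**What to change.** In the last paragraph of SAP 7.9.2.2, replace the by-week ANCOVAs with one MMRM per endpoint. Include week, treatment, region, week-by-treatment, baseline and baseline-by-week, with unstructured covariance and a pre-stated fallback such as heterogeneous Toeplitz. Take the weekly comparisons with placebo from that model, and list these weekly analyses in SAP Section 8 as an addition to the protocol.

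The cost is SAP wording and adaptation of a model type already in use. In the random and baseline-driven scenarios the two methods agreed to within 0.005, so nothing is given up in bias there. There are two downsides: a 12-week unstructured matrix may not converge, hence the fallback, and the covariance would differ from the compound symmetry used for pain and CSBM unless that is aligned too.

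If the ANCOVAs are kept, the minimum is to label them descriptive, name these endpoints in the multiple imputation of SAP 7.9.1.2, and make the Section 8 entry.
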